3. QOL

- a. Global: compare SF-36 scores and sub-scales (73), EQ-5D. (71, 74)
- b. Disease-specific: compare urinary, bowel and prolapse scales of PFIQ score (65)

4. Participants' Perception of Motivation and Barriers to Continued Study Participation questionnaire

8.2 Safety and Other Assessments

Perioperative measures of morbidity include operative time (a risk factor for operative morbidity), estimated blood loss, and intra-operative and post-operative complications. Complications will be categorized using a modification of the Dindo Classification (77). Perioperative morbidity will be recorded at the completion of the surgery, at hospital discharge, and at the 2-week postoperative visit.

In addition, the following specific adverse events will be assessed and reported:

1. Intra-operative ureteral injury/obstruction (identified as no spill of urine from one or both ureteral orifices after prolonged observation (> 10 minutes) via cystoscopy; when indicated, other procedures may be used diagnostically or therapeutically, such as ureteral stent placement.)
2. Removal/replacement of vault suspension sutures to relieve intra-operative ureteral obstruction
3. Postoperative ureteral injury (delayed recognition)
4. Intra-operative neural injury (as determined by post-operative neuropathic pain or other neurologic sequelae) that was new onset: Neuropathic pain attributable to the vaginal vault suspension will be defined as "Acute-onset pain involving the buttock, groin and/or lower extremity, usually unilateral, occurring on the side or sides where vault suspension stitches have been placed and within one week of the index surgery requiring an alteration of routine postoperative care (e.g., nerve block, physical therapy, return to OR for suture removal, the addition of medications used to treat neuropathic pain such as anticonvulsants or tricyclic anti-depressants, or the increase or persistence of narcotic pain medication use beyond 14 days after surgery)."
5. Transfusion of blood products (e.g., whole blood, packed red blood cells, platelets)
6. Vaginal granulation tissue requiring treatment
7. Vaginal or perineal stricture (i.e., narrowing or scarring) prompting a treating physician to suggest or the participant to request treatment (surgical or non-surgical)
8. Rectal injury
9. Postoperative pain

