1.2 Schema

1.3 Schedule of Activities (SOA)

Procedures	Screening Appt.	Initial Appt. +/- 30 days	MRI Appt. +/- 30 days	Anesthesia Clearance	Randomization	Pre-op	Day of Surgery	2 wk Post-op +/- 5 days	2 m Post-op +/- 10 days	12 m Post-op +/- 10 days	24 m Post-op +/- 30 days
Demographics		X									
Medical history		X									
Surgical history		X									
Randomization				X							
Pre-op with surgeon					X						
Inclusion/exclusion criteria	X										
Research consent		X									
Surgical consent						X					
Surgical procedure							X				
Surgeon's Report							X				
Physical exam	X							X	X	X	X
Dynamic pelvic ultrasound	X								X	X	X
MR defecography			X								
Anesthesia Clearance				X							
Bowel habit	X							X	X	X	X
POPQ assessment	X								X	X	X
PFDI assessment	X								X	X	X
Pain scale	X							X	X	X	X
Pain medication use	X							X	X	X	X
Activity scale	X							X	X	X	X
Impression of improvement									X	X	X
PFIQ									X	X	X
SF-36								X	X	X	X
EQ-5D									X	X	X
Brink scale									X	X	X
Research Participation											X
Adverse event/unanticipated problems			X	X	X	X	X	X	X	X	X

2. Introduction

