4.1 Overall Design

This is a collaborative multi-center 2-arm clinical trial comparing: a) transvaginal sacrospinous rectopexy (TSR) with and without conventional vaginal prolapse surgery (CVPS); vs. b) laparoscopic abdominal ventral rectopexy (LAVR) with and without conventional vaginal prolapse surgery (CVPS) for ODS. A standardized common protocol for enrollment, treatment and data collection will be employed by the Clinical Sites and coordinated by the Data Coordinating Center (DCC). Women with and without vaginal prolapse who report OD symptoms in more than 50% of their bowel movements with significant rectal hypermobility (more than 50% compression ratio in dynamic posterior compartment ultrasound) will be approached for eligibility, consent, and enrollment. Participants who meet eligibility criteria and have provided informed consent will be randomly assigned to either abdominal or transvaginal rectopexy procedure (12, 62-64). Prior to randomization, eligible participants will undergo chart review by the anesthesiologist to ensure medical eligibility for both procedures.

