6.1 Study Intervention(s) Administration

6.1.1 Study Intervention Description

Transvaginal Sacrospinous Rectopexy Surgical Technique

The posterior vaginal wall dissection is started with a horizontal incision in the mid-posterior vaginal wall. Dissection is carried down to the sacrospinous ligament (SSL) bluntly on each side. Sacrospinous ligament sutures are placed using a push-and catch suturing device (Capio Slim, Boston Scientific Corporation, USA) to deliver a single 0-polydioxane suture (Monodek, Teleflex Medical OEM) into each ligament approximately 2-2.5 cm medial to the ipsilateral ischial spine (Figure 5). With one finger inside the rectum, the suture is passed through the lateral rectal ligament and rectal muscularis layer, as a two-bite running suture, at a point 7-8 cm cephalad to the anal verge. After tying down the knot on the first side, rectal suture placement is then performed on the contralateral side; this sequential suturing and tying down of left and right sided rectal suspensions allows for assessment and fine-tuning of the rectal suspension and avoidance of excess tension or stretching of the rectal wall. After suspension of the rectum bilaterally, three additional interrupted 0 polydioxane sutures are used to reattach the midline posterior vaginal wall to the midline anterior rectal wall at the same level (7-8 cm cephalad from the anal verge); these sutures provide reinforcement and tension relief to the midline rectum between each lateral SSL suspension suture and serve to close a potential enterocele space.

[figure not shown]

Figure 5: This computational 3D model is created based on MRI images of a normal nulligravid healthy volunteer. The suturing sites on rectum and sacrospinous ligament used for transvaginal sacrospinous rectopexy and related landmarks are demonstrated here in coronal (A) and sagittal (B) views

Laparoscopic Abdominal Ventral Rectopexy Surgical Technique

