The surgery is performed under general anesthesia with patient in steep Trendelenburg position. Usually 4 ports are created. Supra-umbilical port is used as camera port. The rectosigmoid junction is identified and retracted to the left. A "J shaped" peritoneal incision is given extending from the sacral promontory to the anterior peritoneal reflection distally. Right hypogastric nerve and ureter are identified and safeguarded. With combined blunt and sharp dissection, a wide plane is developed in the Rectovaginal/rectovesical space. Any posterior rectal mobilization or lateral dissection is avoided at this stage. A strip of Prolene mesh (Ethicon Endosurgery, Blue Ash, Ohio, United States), trimmed to 3 cm x 17 cm, is prepared and inserted into the pelvic cavity. One end of mesh is fixed to the anterior surface of the distal most part of the rectum using polypropylene sutures. Similarly, it is fixed to the lateral borders of the rectum. Care is taken to avoid full thickness bite into the rectal wall in order to prevent mesh contamination. Finally, the proximal end of mesh is fixed to the sacral promontory using same sutures. Proximal traction on the rectum is avoided while fixing the mesh. The peritoneum is then re-approximated to completely cover the mesh.

Conventional Vaginal Prolapse Surgery

To minimize the number of confounding variables and reduce the complexity of analysis, types of conventional vaginal prolapse surgery will be limited to the following:

1. Vaginal prolapse repair surgery –
 - a. Anterior vaginal repair surgery
 - b. Posterior vaginal repair surgery
 - c. Vault suspension
2. Abdominal prolapse repair surgery –
 - a. Sacrocolpopexy
3. Tension-Free Vaginal Tape

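### The only working definition of neuropathic pain in Section 8.2 is tied to vault suspension stitches, so pain from the sacrospinous sutures of the transvaginal rectopexy cannot meet it when no vault suspension was done

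*Combined protocol and SAP*

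**What the plan says.** Section 8.2 names nine specific adverse events to be assessed and reported. Item 4 is new-onset neural injury during the operation, recognised by neuropathic pain afterwards or by some other neurological consequence. One working definition follows. It opens "Neuropathic pain attributable to the vaginal vault suspension will be defined as" and describes acute pain in the buttock, groin or leg, "usually unilateral, occurring on the side or sides where vault suspension stitches have been placed and within one week of the index surgery", that calls for a change to routine aftercare. Item 2 is worded in the same terms: "Removal/replacement of vault suspension sutures to relieve intra-operative ureteral obstruction".

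Section 6.1.1 describes the two randomised operations and the permitted additional ones. For TSR, "Sacrospinous ligament sutures are placed using a push-and catch suturing device", one suture into each ligament, and each suture is then used to suspend the rectum. The surgical SOP in Appendix C repeats this. "Vault suspension" appears separately in Section 6.1.1, in the list of conventional vaginal prolapse operations, beside anterior and posterior repair. Under Section 4.1 either rectopexy may be done with or without such surgery, as indicated for the individual.

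Section 4.1 makes the comparison of complications between the two rectopexies a secondary objective, and Section 3 lists efficacy and safety as a secondary outcome.

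**The concern.** The definition is attached to an operation that is not under test. The trial compares two ways of suspending the rectum, and the novel one depends on ligament sutures on both sides. The single nerve-pain event with a stated site, onset window and care threshold refers to the stitches of a concomitant procedure that some participants in either arm will have and others will not.

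This bears on the safety comparison. Section 2.1 presents TSR as having shown no significant morbidity so far, and Section 4.2 shows that this experience is a case series of 20 patients. The randomised trial is where suture-related nerve pain after TSR should be measured on a fixed rule. If the reported rate is built from the stated definition, it will partly reflect who had a vault suspension and not which rectopexy was assigned.

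**Working it through.** The plan gives no figure to reproduce, and the point rests on no power or rate calculation. The check applies the definition literally to each combination of operations that Section 4.1 allows.

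Inputs:
- Attribution and location (8.2, item 4): the pain is attributed to the vault suspension and is found "occurring on the side or sides where vault suspension stitches have been placed and within one week of the index surgery".
- TSR (6.1.1, Appendix C): one suture in each sacrospinous ligament, suspending the rectum.
- Laparoscopic abdominal ventral rectopexy, LAVR (6.1.1, Appendix C): mesh sutured to the rectum and to the sacral promontory.
- Vault suspension (4.1, 6.1.1): a separate, optional operation in either arm.

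| Operation received | Vault suspension stitches present? | Can rectopexy-related pain meet the definition? |
|---|---|---|
| TSR, no vault suspension | No | No |
| TSR with vault suspension | Yes | The location can be met, but the pain must be attributed to the vault suspension |
| LAVR, no vault suspension | No | No |
| LAVR with vault suspension | Yes | Same as row 2 |

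So the defined event follows the concomitant vault suspension and not the randomised procedure.

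The item can then be read in two ways:
1. If the working definition governs the count, rectopexy-suture pain is left out.
2. If the broader parent item governs, that pain can be included, but with no stated site, onset window or change-in-care threshold. Classification then rests with the examining clinician, who also judges relatedness (8.3.3.2). Section 6.3 says that surgeons cannot be masked, and Section 6.2.1 assigns TSR to urogynecologists and LAVR to colorectal surgeons. Unguided classification could therefore differ by arm.

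Size: up to 120 participants with equal allocation gives 120 / 2 = 60 assigned to TSR, all due to have bilateral sacrospinous sutures. Events certain to fail the definition = (TSR participants without vault suspension) x (their rate of otherwise qualifying pain from rectopexy sutures). The documents give neither term, so no number is offered.

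**The case against.** The strongest reply is that the listed event is the parent item, new-onset neural injury, which is not limited to any procedure; the vault suspension sentence defines only one subset. That is correct. A reader might infer that nerve pain after TSR would go unrecorded, and the documents do not support this. Section 8.3.4 requires every adverse event to be documented whatever its cause, item 9 lists postoperative pain, and Section 9.4.4 summarises events through 24 months. What these provisions lack is a standard rule. Item 9 is undefined, and the Pain Scale in Appendix D asks about intensity and not about site or cause.

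A second reply is that inclusion criterion 4 requires planned prolapse surgery, so vault suspension might be near universal. It does not close the gap. The permitted surgery may be an anterior or posterior repair or a sacrocolpopexy alone, and Section 4.1 also describes enrolling women without prolapse.

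Three further inferences are tempting and fail:
- *That the clause on narcotic use beyond 14 days cannot be judged because of the visit window ("2 wk Post-op +/- 5 days").* The visit can fall before day 14, but the specific adverse events carry no 2-week cut-off. Events are asked about at every visit, and current narcotic use is asked again at 2, 12 and 24 months. The clause is also only one of several examples of changed care.
- *That the side condition excludes bilateral pain.* The text allows one side or both. The restriction lies in the reference to vault suspension.
- *That item 2 loses ureteral obstruction caused by a rectopexy suture.* Item 1 counts intra-operative ureteral injury or obstruction whatever its cause. Only the removal or replacement of the suture goes unnamed.

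**Conclusion.** The point holds as a gap in the definition. Pain from the TSR sutures cannot meet the stated neuropathic-pain definition when no vault suspension was done, and when one was done it qualifies only if attributed to that procedure. A count made from that definition would miss such events, chiefly in the TSR arm. The word chiefly rests on the assumption that sacrospinous sutures can produce pain of the kind described. Every TSR patient has those sutures as part of the assigned operation, whereas no LAVR patient has them as part of hers.

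A reader might conclude that the reported nerve-injury rate for TSR is already biased downward. The documents do not establish that. No section says the rate will be counted from the working definition alone, and LAVR patients without vault suspension cannot meet it either. The size is unknown for the reasons shown in the working. The case for a change does not depend on it, because the stated rule does not address the procedure being compared.

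**What to change.** In Section 8.2, item 4, replace the attribution in "Neuropathic pain attributable to the vaginal vault suspension will be defined as" with attribution to any suspension or fixation suture or mesh placed at the index surgery, whether for rectopexy or vault suspension. Replace the reference to vault suspension stitches in the location phrase in the same way. Keep the pain sites, the one-week onset and the change-in-care requirement. Section 6.1.1 gives no side for the LAVR fixation at the promontory, so word the location phrase so that this fixation can satisfy it. Apply the definition identically in both arms and record on the adverse event form which suture or mesh is suspected. For consistency, make item 2 refer to rectopexy or vault suspension sutures.

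If participants have already had surgery, reclassify their recorded events under the new wording so that one rule covers the whole trial.

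The cost is an amendment to the protocol and the adverse event form. Treatment, sample size and the primary endpoint are unaffected. The downside is that the reported event rate, especially for TSR, may rise.

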7.3 Lost to Follow-Up

A participant will be considered lost to follow-up if she fails to return to any scheduled visits and is unable to be contacted by the study site staff.

The following actions must be taken if a participant fail to return to the clinic for any required study visit:

- The site will attempt to contact the participant and reschedule the missed visit within 30 days and counsel the participant on the importance of maintaining the assigned visit schedule and ascertain if the participant wishes to and/or should continue in the study.
- Before a participant is deemed lost to follow-up, the investigator or designee will make every effort to regain contact with the participant (where possible, 3 calls/messages and, if necessary, a certified letter to the participant's last known mailing address or local equivalent methods). These contact attempts should be documented in the participant's medical record or study file.
- Should the participant continue to be unreachable, he or she will be considered to have withdrawn from the study with a primary reason of lost to follow-up.

8. Study Assessments and Procedures

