Pain scale and pain medication use assessment will be completed by the research personnel during screening, 2-week, 2-month, 12-month, and 24-month post-operative appointments. Participants will be asked to rate the average amount of pain within the past 24 hours while at rest, with normal activities, with exercise, and worst pain of the today. All items use the format with a response scale from 0 (no pain sensation) to 10 (most intense pain imaginable). Then the participant will be asked if they are currently taking narcotic pain medication.

Activity Scale

Activity scale will be completed by the research personnel during screening, 2-week, 2-month, 12-month, and 24-month post-operative appointments. Participants will be presented with 13 activities in which they will be asked to rate how difficult it was for them to perform them in the past 24 hours. The rating will be 1 (no difficulty), 2 (a little difficulty), 3 (some difficulty), 4 (a lot of difficulty), 5 (not able to do it), and 6 (did not do it for other reasons). Then, participants will be asked 5 additional questions regarding activity in the past month.

Impression of Improvement

Impression of improvement assessment will be completed by the research personnel during 2-month, 12-month, and 24-month post-operative appointments. Participants will be asked to indicate a number that best describes their current post-operative condition in comparison to how it was pre-operatively. The rating will be 1 (very much better), 2 (much better), 3 (a little better), 4 (no change), 5 (a little worse), 6 (much worse), and 7 (very much worse).

Pelvic Floor Impact Questionnaire (PFIQ)

PFDI assessment will be completed by research personnel during 2-month, 12-month, and 24-month post-operative appointments. The PFIQ-7 consists of 7 questions that need to be answered 3 times each considering symptoms related to the bladder or urine, vagina or pelvis, and bowel or rectum and its effect on function, social health, and mental health in the past 3 months. The responses for each question range from 0 (not at all) to 3 (quite a bit). To get scale scores, the mean of each of the 3 scales is individually calculated, which ranges from 0-3. This number is then multiplied by 100 and then divided by 3. The scale scores are then added together to get the total PFIQ-7 score, which ranges from 0-300.

Short Form (SF) - 36

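### The current-use narcotic question, asked at a 2-week visit allowed on days 9 to 19, captures poorly the adverse-event trigger of narcotic use beyond day 14

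*Combined protocol and SAP*

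**What the plan says.** Section 8.2 defines neuropathic pain attributable to the vaginal vault suspension as acute-onset pain arising "within one week of the index surgery requiring an alteration of routine postoperative care (e.g., nerve block, physical therapy" and other examples. The last example is "or the increase or persistence of narcotic pain medication use beyond 14 days after surgery". The same section records perioperative morbidity for the last time at the 2-week visit, and lists the specific adverse events separately.

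The Schedule of Activities (Section 1.3) and the Schedule of Forms (Appendix E) give that visit the same window: "2 wk Post-op +/- 5 days". The 2-month visit has a window of 10 days either side.

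The SOP on Study Assessments and Measurements (Appendix D) describes the narcotic item: "Then the participant will be asked if they are currently taking narcotic pain medication". It describes no date, dose or change in use. The item is asked at screening, 2 weeks, and 2, 12 and 24 months. The pain ratings on the same form cover the past 24 hours, and the 13 activity items ask "how difficult it was for them to perform them in the past 24 hours".

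Section 3 makes postoperative pain, with pain-medication use, the first item under the efficacy and safety comparison. Section 7.3 tells sites to try to "reschedule the missed visit within 30 days", without saying from which day the 30 days run. The mixed model in Sections 9.4.2 and 9.4.3 lists baseline characteristics and surgeon, but not the actual day of the visit.

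**The concern.** The criterion turns on what happens after day 14, and day 14 is the middle of the window for the only early visit. A current-use question on day 10 or 12 cannot tell whether the woman will still be using narcotics on day 15. By the 2-month visit the same question no longer shows whether she did. Nor can a yes/no answer show an increase, which the definition also mentions.

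The pain-medication secondary outcome has a related weakness. The share answering yes at 2 weeks depends on the day each woman is asked, in a period when many will be stopping. The 24-hour pain and activity scores share this dependence on visit day. Two weeks is the only scheduled assessment of these outcomes before 2 months, and the transvaginal operation is presented as the less invasive one, so readers will look closely at these early results.

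**Working it through.** The plan gives no figure for this point, so there is none to reproduce. The check is day arithmetic on the stated windows.

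**Inputs.** 14-day cut-off (Section 8.2); 2-week window of 5 days either side and 2-month window of 10 days either side (Section 1.3); current-use item (Appendix D SOP); 30-day rescheduling (Section 7.3).

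1. *2-week window.* 14 − 5 = 9 and 14 + 5 = 19, so days 9 to 19, which is 11 days.
2. *Days on which use beyond day 14 cannot yet exist.* Days 9 to 14 are 6 days; 6/11 = 55% if visits are spread evenly. If visits instead cluster normally around day 14 and are truncated to the window (an assumption), the share on or before day 14 is 70%, 60%, 57% and 56% for standard deviations of 1, 2, 3 and 4 days.
3. *Next narcotic question.* With 2 months taken as 61 days, 61 − 10 = 51 and 61 + 10 = 71. With 60 days the window is 50 to 70.
4. *What the item can show.*
   - Visit on days 9 to 14: neither answer establishes whether narcotics were used after day 14.
   - Visit on days 15 to 19: a yes shows use beyond day 14. A no does not exclude use that ended between day 15 and the visit.
   - Visit at 2 months: a yes shows current use. A no says nothing about use that ended earlier.
5. *Example.* A woman seen on day 12 who stops on day 25 answers yes, then no. A woman seen on day 12 who stops on day 13 gives the same two answers. The first used narcotics beyond day 14 and the second did not; the item cannot separate them.
6. *Rescheduled 2-week visit.* 14 + 30 = day 44 if counted from the target day; 19 + 30 = day 49 if counted from the end of the window. Either is close to the start of the 2-month window. The documents do not say which reading applies or how such a visit would be labelled.

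**The case against.** The strongest reply is that the adverse-event system is a second route. Under Section 8.3.4 investigators ask at every visit about events since the last one, record onset and resolution, and follow events to resolution. The definition requires pain starting within a week of surgery, so an affected woman may already have an open adverse event at her 2-week visit. Nothing says that this event is scored from the narcotic item. This stands: a reader might infer that the criterion is unobservable, and the documents do not support that. What remains is that the dates described belong to the event, not to narcotic use, so the 14-day limb rests on recall or chart review.

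The limb is also narrow. It is one of several example triggers, and the quoted definition concerns pain attributed to vault suspension, which not every participant will have. Form 07, the 2-week visit form, is not shown and may already hold narcotic dates. Both points stand.

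A reader might also take the 2-week visit to be allowed up to day 44. The window is days 9 to 19 in both schedules; Section 7.3 is a rule for missed visits with no stated starting day.

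Finally, a reader might infer that the 2-week comparison is biased. If narcotic use stopped exponentially with a median of 7 days, mean visit days of 11 and 16 in the two arms would give 0.5^(11/7) = 34% against 0.5^(16/7) = 21%, a spurious 13 points (11 to 14 for medians of 5 to 10 days). But the curve, the median and the 5-day gap are all assumed. Different specialties operate in the two arms, yet the follow-up assessments are made by research personnel under one common protocol. Without arm-dependent timing, spread in visit day adds noise rather than bias. The Activity Scale also has five questions on the past month, which depend less on the exact day.

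**Conclusion.** The point holds as a measurement weakness. The planned narcotic item cannot establish use beyond day 14 at visits on 6 of the 11 permitted days, and use that ends before the 2-month visit can go unrecorded by it. The 55% is a share of calendar days under even spacing (56% to 70% if visits cluster around day 14). It is not a share of women or of missed events, and the documents give no basis for estimating the number of events missed.

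The consequence is limited to one trigger of one adverse event and to the pain-medication secondary outcome, with added noise in 2-week pain and activity scores. Bias between arms would need visit timing to differ by arm, which the documents do not show. The primary endpoint is unaffected. The change is worth making because it costs almost nothing now, while dates not collected may be hard to recover later. The conclusion assumes that Form 07 does not already record them.

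**What to change.** 1. Add the date of last narcotic use, and the date of any increase, to the existing pain form (Form 09) at 2 weeks and 2 months. Score the 14-day criterion from these dates. A woman still using narcotics at an early 2-week visit is then resolved at 2 months.
2. For the secondary outcome, report narcotic use at a fixed day, such as day 14, instead of at whatever day the visit took place.
3. State in Section 7.3 from which day the 30 days run and how a rescheduled visit relates to the windows in Section 1.3.
4. In the SAP, which Section 9.4.1 leaves to be completed before database lock, add a sensitivity analysis of 2-week pain and activity by actual days since surgery. Keep all randomised women in the main comparison: dropping those seen outside days 9 to 19 would select on something that happens after randomisation.

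The cost is one or two form fields, a sentence in Section 7.3 and a little analysis work. Dates recalled at 2 months will carry some error. If Form 07 already holds the dates, a cross-reference to it replaces the new fields.
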